8. TIMEPOINT OF RELEASE OF TREATMENT INFORMATION

The treatment information will be released for interim analysis according to the details specified in the logistics plan.

Once the last patient has completed their *End-of-Treatment (EOT) visit* and all corresponding data has been entered and cleaned to the level documented in the "Data Delivery Request" (DDR) form, the data will be declared ready to be unblinded via the "Data Ready to be Unblinded and/or Final Trial Closure Notification" (RUN) form. Then the treatment information will be released for analysis.

The data collection for the off-treatment residual effect period until the End-of-Study (EoS) / Follow-Up visit will continue into the unblinded trial database. Once trial data collection has been completed and all data has been entered and cleaned as documented on the RUN form, a final data lock will be performed.

After the release of treatment information, it is expected that only trial data related to the off-treatment residual effect period will be entered and changed. Therefore, after the timepoint of release of treatment information, all changes affecting trial data up to the End-of-Treatment (EoT) visit will be documented and summarized in the CTR.

Proprietary confidential information © 2024 Boehringer Ingelheim International GmbH or one or more of its affiliated companies.

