# 4.1.4 Blinding and procedures for unblinding

# 4.1.4.1 Blinding

#### Part 1 (Phase IIb)

Trial participants, investigators, central reviewers, and everyone (except for specified project members [e.g. PK]) involved in trial conduct or with any other interest in this double-blind trial will remain blinded regarding the randomised treatment assignments until the database is declared ready for final analysis according to the sponsor's SOPs.

Further details, regarding the timepoint of unblinding the database for analyses including primary, interim, and final analysis, are documented in the TSAP or logistics plan.

The randomisation codes will be provided to bioanalytics before the last trial participant completed the visit of Phase IIb (Part 1) of the trial to exclude placebo samples from the PK and ADA analysis. Bioanalytics will not disclose the randomisation code or the results of their measurements until the database lock.

For the primary analysis at and interim analysis at a respective team ("shadow team") independent of the main trial team will be formed to conduct the necessary analysis and reporting steps and ensure to maintain the blind and restrict access to the randomisation codes from the main trial team. Details of data transfer, timelines, and involved trial functions during this process will be described in a separate logistics plan which will also specify details on data access.

Page 63 of 177

Proprietary confidential information © 2023 Boehringer Ingelheim International GmbH or one or more of its affiliated companies

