#### 7.2.8 Interim analyses

The primary analysis for Part 1 will be conducted after the last trial participant completes the visit. A respective team ("shadow team") independent of the main trial team will be formed to conduct the necessary analyses and ensure to maintain the blind and restrict access to the randomisation codes from the main trial team. Details of this process will be described in a separate logistics plan which will also specify details on data access. The trial team members, trial participants, and investigators will remain blinded until the end of Part 1. The sponsor will make a decision for proceeding into Part 2 (Phase III). This recommendation will include the selection of appropriate dose(s) for Part 2 and may also include modification to inclusion/exclusion criteria, sample size and endpoints. The sponsor intends to seek health authority feedback on the cumulative data available after Part 1
assess the benefit/risk of spesolimab in HS.
The for Part 1 will be conducted after the last trial participant completes the visit and the efficacy effect size will be evaluated. Trial participants and investigators will remain blinded until the end of this study part.
No adjustment of the family-wise Type I error for Part 2 is needed after Part 1 (Phase IIb), as

the analysis sets of Part 1 (Phase IIb) and Part 2 (Phase III) are independent.

Page 114 of 177

Proprietary confidential information © 2023 Boehringer Ingelheim International GmbH or one or more of its affiliated companies

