7. PLANNED ANALYSIS

The primary objective for dose finding Phase IIb (Part 1) are as follows:

- (1) to demonstrate a non-flat dose response curve, evaluate the quantitative treatment effect size, and evaluate the dose-response relationship based on the primary endpoint of percent change from baseline in dT count at Week 8;
- (2) to determine an optimal dose candidate for Part 2 by incorporating information of available safety and of efficacy based on the primary endpoint of percent change from baseline in dT count at Week 8.

The primary and interim analysis for Part 1 will be conducted after the last trial participant completes the Week 8 visit and Week 16 visit respectively. Final trial analysis is planned to be performed at the end of the study once all randomized patients have completed the study (including any follow-up period). If applicable, details of biomarker analyses will be provided in a separate Biomarker Statistical Analysis Plan.

For End-Of-Text (EoT) tables, the set of summary statistics is: N / Mean / SD / Min / Median / Max.

For tables that are provided for endpoints with some extreme data, median, quartiles and percentiles should be preferred to mean, standard deviation, minimum and maximum.

Tabulations of frequencies for categorical data will include all possible categories and will display the number of observations in a category as well as the percentage (%) relative to the respective treatment group (unless otherwise specified, all subjects in the respective subject set regardless of whether they have non-missing values or not).

The precision for percentages should be one decimal point, unless the denominator is smaller than 100 (in all treatment columns), in which case percentages are given in integer numbers. The category missing will be displayed only if there are actually missing values.

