7.8.1 Adverse Events

Date: 07-08-2024, Version 1.0

Unless otherwise specified, the analyses of AEs will be descriptive in nature, which will include all on-treatment events up to week 8, week 16 treatment, as well as all events during the whole on-treatment period respectively. All analyses of AEs will be based on the number of subjects with AEs and NOT on the number of AEs.

AEs will be coded with the most recent version of MedDRA®. Patients will be analyzed according to the actual treatment received.

The analysis of AEs will be based on the concept of treatment emergent adverse events (TEAE). That means that all AEs occurring between first drug intake till 112 days after last drug intake will be assigned to the on-treatment period. All AEs occurring before first drug intake will be assigned to 'screening' and all AEs occurring after last drug intake + 112 days will be assigned to 'follow-up' (for listings only). For details on the treatment definition, see Table 6.1:1.

The exposure adjusted incidence rate (per 100 patient years) of a selected treatment emergent adverse event is defined as the number of patients experiencing the adverse event per

Proprietary confidential information © 2024 Boehringer Ingelheim International GmbH or one or more of its affiliated companies.

treatment group during time at risk divided by the total time of patients at risk in that treatment group to contribute the event to the analysis multiplied by 100 (per 100 patient years).

Time at risk [patient years] = (date of onset of AE– first treatment start date within that treatment period + 1) / 365.25

If, for a patient, the selected treatment emergent adverse event didn't occur during the above defined treatment period (per Table 6.1:1) then the time at risk will be censored at the earliest of date of death, last contact date per EoS page, or the end of the above defined treatment period.

For each selected treatment emergent AE, the exposure adjusted incidence rate will be calculated as:

Incidence rate [1/100 Patient years (pt-yrs)] = 100 * number of patients with TEAE / Total TEAE-specific time at risk [patient years].

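### SAP Section 8 opens the database while treatment-emergent adverse events are still being collected, and its rule on documenting changes stops short of them

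*SAP*

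**What the plan says.** - **Release point.** SAP Section 8 sets the trigger as follows: "Once the last patient has completed their *End-of-Treatment (EOT) visit* and all corresponding data has been entered and cleaned to the level documented" in the delivery request, the data are declared ready. "Then the treatment information will be released for analysis".
- **Collection after release.** "The data collection for the off-treatment residual effect period until the End-of-Study (EoS) / Follow-Up visit will continue into the unblinded trial database".
- **Change rule.** Section 8 expects only data from that period to be entered or altered after release. On that ground it asks that "all changes affecting trial data up to the End-of-Treatment (EoT) visit will be documented and summarized in the CTR".
- **Blinding in the protocol.** Section 7.2.8: "The trial team members, trial participants, and investigators will remain blinded until the end of Part 1". Section 4.1.4.1 (Part 1) says that those involved "will remain blinded regarding the randomised treatment assignments until the database is declared ready for final analysis", and leaves the detail of the unblinding timepoint to the SAP or a logistics plan.
- **Final analysis.** SAP Section 7 schedules it only after every randomised participant has finished, follow-up included.
- **Adverse event window.** SAP 7.8.1: "all AEs occurring between first drug intake till 112 days after last drug intake will be assigned to the on-treatment period". SAP Table 6.1:1 starts the off-treatment period at last dose + 113 days. Protocol 7.2.6 sets the same window as a residual effect period of 16 weeks. Occurrence of treatment-emergent adverse events (TEAEs) is the Part 1 secondary safety endpoint (protocol 2.1.3, SAP 5.2.2).
- **Follow-up.** Protocol Section 6 puts the End-of-Study (EoS) visit 112 days after the last dose or 98 days after EoT. Participants who roll over have EoT and EoS on the same date and no safety follow-up here.

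**The concern.** Section 8 handles the time between EoT and EoS as if it lay outside treatment. Every section that defines the adverse event window puts nearly all of it inside. Two things follow.

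First, part of a secondary endpoint would be entered, queried and cleaned with treatment assignments available. The sponsor does the data management (protocol 8.7) and the company causality assessment (protocol 8.4), and protocol 5.2.6.1.6 lists a dose-response pattern as an argument for causality. Knowing the arm can change how hard an event is queried, or how its dates and terms are settled.

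Second, the safeguard Section 8 offers, a summary in the trial report of changes made after release, stops at EoT. It does so on the premise that only off-treatment data can still change, and by the SAP's own definitions that premise is false. Edits to late TEAEs fall outside it.

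At stake is the credibility of the final safety comparison between the originally randomised arms.

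**Working it through.** **1. Reproduce the window.** 16 weeks × 7 = 112 days, so the protocol and SAP windows agree.

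**2. How much of it follows EoT.** From protocol Section 6:
- last dose to EoT = 112 − 98 = 14 days
- window left after EoT = 112 − 14 = 98 days, and 98/112 = 87.5%
- with the ±3-day EoT visit window: 95 to 101 days, or 85% to 90%

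This is a ceiling, because release also waits for data cleaning.

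**3. Same days, two descriptions** (participant who does not roll over):

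| Interval | Table 6.1:1, SAP 7.8.1, protocol 7.2.6 | SAP Section 8 |
|---|---|---|
| Last dose to EoT (about 14 days) | On-treatment | Changes after release documented |
| EoT to last dose + 112 days (about 98 days) | On-treatment, TEAE | Called off-treatment; unblinded database once codes are released; changes not covered |
| From last dose + 113 days | Off-treatment | Off-treatment |

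The conflict is confined to the middle row.

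**4. How many participants, and how much time.** The documents give neither the number not rolling over nor a visible treatment duration or recruitment period, so this is an illustration. Assumptions:
- even recruitment over M = 6 to 18 months of 30.4 days
- release L days after the last EoT, with L = 0, 28 or 56
- EoT at week T, with T = 40 to 52. The lower end comes from the visit schedule: Visit 19 is about 6 months (26 weeks) from baseline by the South Africa tuberculosis footnotes, and 12 dosing visits (20 to 31) follow. Even at weekly spacing the last dose is no earlier than week 26 + 12 = 38, and EoT no earlier than week 40.

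Formulas, for completers who do not roll over:
- share still in the window at release = (98 − L)/(30.4 × M)
- mean days left for those = (98 − L)/2
- on-treatment window = (T − 2) + 16 = T + 14 weeks, which is 378 days at T = 40 and 462 days at T = 52
- share of pooled on-treatment time after release = share × mean days / window

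| L (days) | Share, M = 6 | Share, M = 18 | Mean days left | Share of on-treatment time |
|---|---|---|---|---|
| 0 | 98/182.4 = 54% | 98/547.2 = 18% | 49 | 1.9% to 7.0% |
| 28 | 70/182.4 = 38% | 70/547.2 = 13% | 35 | 1.0% to 3.6% |
| 56 | 42/182.4 = 23% | 42/547.2 = 8% | 21 | 0.3% to 1.3% |

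In the last column the low end uses M = 18 and T = 52, and the high end M = 6 and T = 40. Example: 0.537 × 49/378 = 7.0%. Over the whole Part 1 population the share is smaller again, because participants who roll over contribute nothing.

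**5. After the fix.** If adverse-event staff stay blinded to the last EoS visit, none of the 112 days is handled by unblinded staff.

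**The case against.** The other side has a fair case.

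- **Delegation.** Protocol 4.1.4.1 hands the unblinding timepoint to the SAP, and Section 8 is that text. A defined release point is therefore not wrong in itself. But what is delegated is detail. It does not license a conflict with protocol 7.2.8 or with the SAP's own period definitions, and SAP Section 4, which lists departures from the protocol's analyses, mentions none on blinding.
- **The end of Part 1 is not defined.** True. Reading it as the last Part 1 visit is an inference, though the natural one: protocol 8.6 ends the trial at the last participant's last visit, and SAP Section 7 runs the final analysis after follow-up.
- **Codes are released for analysis only.** A reader might infer that investigators are unblinded and that site grading or causality is compromised. The documents do not say so. Severity is graded by CTCAE at site, and SAP 7.8.1 tabulates relatedness as judged by the investigator. What remains exposed is work on the sponsor side. For the Week 8 and Week 16 analyses a shadow team is named; for this release Section 8 names neither such a team nor any limit on access.
- **Little dose contrast is left.** Placebo participants move to spesolimab at Visit 14, the low-dose group may be up-titrated, and from Visit 10 the high and medium groups share one maintenance category (protocol 3.1). Safety is descriptive, without testing. All this stands and limits the consequence.
- **Edits remain traceable.** Protocol 8.3.1 requires an audit trail. The gap is in what the trial report must summarise, not in traceability.

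**Conclusion.** The inconsistency is real and worth correcting; its likely effect is small. Section 8 mislabels up to 98 of the 112 post-dose days, lets TEAEs from those days enter an unblinded database, and leaves changes to them out of the documented-changes rule. Under the assumptions above, roughly 0.3% to 7% of on-treatment time among completers who do not roll over is collected after release. The true number of participants is unknown. The exposure is to the final descriptive safety comparison of the originally randomised arms.

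Stronger readings are tempting but not supported:
- **Part 2 dose choice.** Protocol 2.1.1 and 8.6 rest it on the primary and interim analyses, which SAP Section 3 places at Weeks 8 and 16. Both precede the last EoT visit.
- **Efficacy.** The Week 8 and Week 16 results are complete before release and are not affected.
- **A large share of the safety window.** That would need a short treatment period, which Visit 19 at about 6 months with twelve dosing visits to follow does not allow.

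**What to change.** In SAP Section 8:

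1. State that staff who query, clean or review adverse events stay blinded until the last EoS visit and the final data lock. If codes are wanted earlier for analysis, limit them to a separate team, such as the shadow team already used at Weeks 8 and 16, and name the purpose.
2. Replace the off-treatment label with wording that matches Table 6.1:1, where off-treatment begins at last dose + 113 days.
3. Extend the documented-changes rule from EoT to all data up to last dose + 112 days.
4. Say what is meant by the end of Part 1, so that Section 8 and protocol 7.2.8 agree.

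The cost is SAP wording plus later access for the main team: up to 98/7 = 14 weeks, less the cleaning time that release already requires. No analysis visible in the SAP falls between the last EoT visit and the final lock. The logistics plan and parts of the SAP cannot be seen, so if an analysis is planned in that gap, the separate team can do it without delay.

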11. HISTORY TABLE

Table 11: 1 History table

Date: 07-08-2024, Version 1.0

Version	Date (DD-MMM- YY)	Author	Sections changed	Brief description of change
1.0	13-08-2024		None	This is the final TSAP.
